### 5.3.2. End Date and Time of the Last Treatment Regimen

The end of the last treatment regimen will be either:

- The date and time of the last rFIXFc dose for patients whose last treatment regimen was prophylaxis, ITI, or if they ended the study in a surgical/rehabilitation period.
- At 23:59 on the day of the last non-safety follow-up study visit for patients whose last treatment regimen was episodic.

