### 5.3.3. Treatment Regimen Changes

In the following sections, new treatment regimen refers to the regimen to which the patient has changed, and the previous treatment regimen refers to the regimen immediately before the new treatment regimen. The start date and time of the new treatment regimen and the end date and time of the previous treatment regimen are defined in the following scenarios:

- From an episodic regimen to a prophylactic regimen: The prophylactic regimen starts at the date and time of the first prophylactic dose in the prophylactic regimen. The episodic regimen ends 1 minute before that. If the time of the first prophylactic dose in the prophylactic regimen is not available, the prophylactic regimen will start at 00:01 on the day of the first prophylactic dose in the prophylactic regimen, and the episodic regimen will end at 23:59 on the day prior to that.
- From a prophylactic regimen to an episodic regimen: The prophylactic regimen ends at the date and time of the last prophylactic dose in the prophylactic regimen. The episodic regimen starts 1 minute after that. If the time of the last prophylactic dose in the prophylactic regimen is not available, the prophylactic regimen will end at 23:59 on the day of the last prophylactic dose in the prophylactic regimen, and the episodic regimen will start at 00:01 on the next day.
- From an episodic regimen to an ITI regimen: The ITI regimen starts at the date and time of the first ITI dose in the ITI regimen. The episodic regimen ends 1 minute before that. If the time of the first ITI dose in the ITI regimen is not available, the ITI regimen will start at 00:01 on the day of the first ITI dose in the ITI regimen, and the episodic regimen will end at 23:59 on the day prior to that.
- From a prophylactic regimen to an ITI regimen: If there is no prophylactic dose on the day of the treatment regimen change recorded in the eCRF, the ITI regimen starts at

	Statistical Analysis Plan	Final v1.0
---	----------------------------------	-------------------

00:01 on the day of treatment regimen change, and the prophylactic regimen ends at 23:59 on the day prior to the day of treatment regimen change. If there is a prophylactic dose on the day of treatment regimen change, the ITI regimen starts 1 minute after that prophylactic dose, and the prophylactic regimen ends on the date and time of that prophylactic dose.

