#### **5.4.2. Efficacy Period**

The efficacy period will be used for the evaluation of efficacy and health outcome endpoints. For a patient to have an evaluable efficacy period over the duration of study, he must have at least 1 day of treatment for an episodic regimen or at least 2 prophylactic injections for prophylactic regimens.

The start and end, and the total duration of the efficacy period for a given treatment regimen is the same as the start and end, and the total duration of that treatment regimen defined in Section 5.3.4 with the exceptions described in the following two subsections. The start of the efficacy period for each patient is the start of their first treatment regimen and the end is the end of their last.

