##### **5.4.2.1. Adjustments Due to Surgical/Rehabilitation Periods**

For analysis purposes, the efficacy period for a given treatment regimen will be adjusted for all surgical/rehabilitation periods (major and minor). The start and end of the efficacy period for a given treatment regimen are adjusted as follows:

	Statistical Analysis Plan	Final v1.0
---	----------------------------------	-------------------

- For patients on a prophylactic regimen before the start of a surgical/rehabilitation period, the efficacy period for the prophylactic regimen continues up to the last dose (for prophylaxis or bleeding) before the start of the surgical/rehabilitation period.
- For patients on the episodic regimen before the start of a surgical/rehabilitation period, the efficacy period for the episodic regimen continues up to 1 minute before the start of a surgical/rehabilitation period.
- For patients on a prophylactic regimen following the end of a surgical/rehabilitation period, the efficacy period for the prophylactic regimen starts or re-starts at the first prophylactic dose following the end of the surgical/rehabilitation period.
- For patients on the episodic regimen following the end of a surgical/rehabilitation period, the efficacy period for the episodic regimen starts or re-starts at 00:01 on the day following the end of the surgical/ rehabilitation period.

Start and end dates/times for the efficacy period for given treatment regimens and treatment regimen changes will be adjusted for each surgery (major or minor) as necessary.

For patients on a prophylactic regimen before the start of a surgical/rehabilitation period, the interval of time between the last dose before the surgical/rehabilitation period and the start of the surgical/rehabilitation period will not be attributed to the efficacy period for the prophylactic regimen. By definition, there should not be any treated bleeding episodes in this interval of time.

For patients on a prophylactic regimen following the end of a surgical/rehabilitation period, bleeding episodes that occur after discharge from a rehabilitation facility but before the next prophylactic dose will be attributed to the surgical/rehabilitation period and hence not counted towards the annualized bleeding rate (ABR).

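### Prophylaxis efficacy time ends at the last rFIXFc dose of any kind, so a late treated bleed extends it while a bleed-free tail is dropped; mean prophylaxis ABR is biased slightly upward

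*SAP*

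**What the plan says.** The rules that set the prophylaxis ABR denominator are these.

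- **Prophylaxis as last regimen (SAP 5.3.2).** It ends at "The date and time of the last rFIXFc dose for patients whose last treatment regimen was prophylaxis". The dose is not limited to prophylactic doses.
- **Episodic as last regimen (SAP 5.3.2).** It ends "At 23:59 on the day of the last non-safety follow-up study visit for patients whose last treatment regimen was episodic", a point that does not depend on bleeding.
- **Switch from prophylaxis to episodic (SAP 5.3.3).** "The prophylactic regimen ends at the date and time of the last prophylactic dose in the prophylactic regimen". Episodic time starts one minute later.
- **Link to efficacy (SAP 5.4.2).** "the total duration of the efficacy period for a given treatment regimen is the same as the start and end" of the regimen, apart from the adjustments for surgery and for large injection intervals.
- **Before surgery (SAP 5.4.2.1, first bullet).** Prophylaxis time "continues up to the last dose (for prophylaxis or bleeding) before the start of the surgical/rehabilitation period". Of the interval left out, the SAP says: "By definition, there should not be any treated bleeding episodes in this interval of time".
- **ABR (SAP 7.4.3).** Bleeds in the efficacy period, divided by days in that period, times 365.25.

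Protocol 10.2.3.4 has bleeds treated with study drug once a child is eligible, so a bleed injection can become the last rFIXFc dose.

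**The concern.** Whether the time after the last regular dose enters the denominator depends partly on the outcome being measured. If a bleed is treated in that tail, the bleed is counted and time runs to its injection. The days after that injection are dropped. If there is no bleed, the whole tail is normally dropped. For the pre-surgery gap, the SAP's own remark that the excluded interval contains no treated bleeds describes this selection.

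The annualized bleeding rate is the first-listed secondary endpoint, reported by regimen. The episodic column has a fixed end and the prophylaxis column does not, so the two are not built alike. The per-patient mean gives a child with a few weeks of prophylaxis the same weight as a child who completes, and the distortion is largest in short exposures.

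**Working it through.** The plan states no figure that depends on this rule, and the sample size rests on clinical grounds (SAP 3.3), so there is nothing to reproduce. The check applies the SAP's ABR formula to a simple model.

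**Inputs**
- Weekly dosing: SAP 3.1.2.2.
- Completion at 50 exposure days: Protocol 10.6. If all are weekly doses, T = 49 × 7 = 343 days.
- True rate λ = 3 per year: an assumption. Protocol 5.1.1 cites as few as 3 to 4 spontaneous bleeds per year on prophylaxis.
- Gap τ from last regular dose to final visit: an assumption of 3, 7 or 14 days. The documents do not give it. The 72-hour washout before inhibitor sampling (Protocol 10.2.4) suggests about 3 days or more, unless the child is dosed at that visit.
- Poisson bleeds with one injection each.

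**One child, 3 bleeds in 343 days, final visit at day 350**
- No tail bleed: the SAP gives 3/343 × 365.25 = 3.19. Counting to the visit gives 3/350 × 365.25 = 3.13.
- A bleed treated on tail day 4: the SAP gives 4/347 × 365.25 = 4.21. Counting to the visit gives 4/350 × 365.25 = 4.17.

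The SAP value is the higher one in both cases.

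**Average bias**

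The expected bleed-free time dropped is (1 − exp(−λτ))/λ, so relative bias ≈ (1 − exp(−λτ))/(λT). For T = 343 and τ = 7:
- λτ = 3 × 7/365.25 = 0.0575, and 1 − exp(−0.0575) = 0.0559
- λT = 3 × 343/365.25 = 2.817
- bias ≈ 0.0559/2.817 = 2.0%

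| T (days) | τ (days) | Formula | Simulated mean of per-patient ABR |
|---|---|---|---|
| 343 | 3 | 0.9% | 3.02 (+0.8%) |
| 343 | 7 | 2.0% | 3.06 (+2%) |
| 343 | 14 | 3.9% | 3.11 (+3.8%) |
| 182 (26 weeks) | 7 | 3.7% | +3.7% |
| 84 (12 weeks) | 7 | 8.1% | about +8% |
| 28 (4 weeks) | 7 | 24.3% | about +22% |

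The formula approximates the pooled rate, so it overshoots the per-patient mean at short T. Across true rates of 1 to 10 per year, with T = 343 and τ = 7, the simulated bias stays between 1.8% and 2.1%. Ending at the last prophylactic dose returns 3.00.

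**Scale**

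The Poisson standard error of a mean ABR of 3 over 343 days is √(3 × 365.25/343/n), which is 0.40 for n = 20 and 0.33 for n = 30. An excess of 0.06 is about one sixth of that.

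**Treatment stopped at 50 exposure days of any kind**

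Bleed injections count as exposure days, so more bleeds bring the stop forward. With rate 3 and a 7-day gap, simulated mean ABRs were:

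| End rule | Run A | Run B |
|---|---|---|
| SAP (last dose of any kind) | 3.13 | 3.12 |
| Final visit | 3.07 | 3.05 |
| Last prophylactic dose | 3.01 | 3.00 |

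The visit-based end keeps 0.07/0.13 = 54% of the excess in run A and 0.05/0.12 = 42% in run B, so about half.

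**The case against.** The strongest reply is that this is immaterial. ABR is descriptive and no hypothesis is tested. For a completer the excess is far below sampling error, and no decision in either document turns on it. The gap length is assumed, and no number of surgeries is given from which to size the pre-surgery part. The convention before surgery is openly stated. All of that stands, and it makes this a minor refinement.

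It can also be said that SAP 7.4.3 already plans ABR for patients with at least 50 exposure days, or at least 26 weeks of dosing, within a regimen, and that medians are reported. Those subsets do leave out the shortest exposures, and the median is less affected. But they keep the same end rule, so a bias of about 2 to 4% for a 7-day gap remains within them. The rule removing intervals over 28 days only caps the extension.

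A reader might infer more than the text supports:
- **That tail time counts only if there is a bleed.** A late training dose or one for another reason also extends it. This does not reverse the direction.
- **That every child ending on prophylaxis has an inflated ABR.** A child with no bleeds has an ABR of 0 under any of these rules, and one whose last regular dose is at the final visit is unaffected. The bias is an average over children.
- **That the rule flatters the product.** It works the other way.
- **That SAP 5.3.3 contradicts SAP 5.3.2.** They cover different situations. On a switch to episodic treatment no time or bleed is lost, because the episodic period takes over at once.

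**Conclusion.** The point holds as a small, systematic upward bias in the mean prophylaxis ABR, caused by an end date that can depend on bleeding. At an assumed 3 bleeds per year it is about 1 to 4% for roughly 50 weekly doses and gaps of 3 to 14 days. With a 7-day gap it is about 8% at 12 weeks and 22% at 4 weeks. The two larger figures describe short exposures and should not be read as the typical effect. How far they move the overall mean depends on how many children have little prophylaxis time, which the documents cannot tell us. The direction follows from the SAP text. The size rests on the assumed rate, the assumed gap and the Poisson model. It is worth correcting because the correction is cheap, not because conclusions are at risk.

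**What to change.** In SAP 5.3.2 and the first bullet of SAP 5.4.2.1, state that for ABR the prophylaxis efficacy period ends at the last prophylactic dose, and that only bleeds up to that time are counted. List treated bleeds after that dose separately, so that they remain visible. Word the change as applying to ABR, because annualized consumption (SAP 6.6.1.4) uses the same efficacy period.

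An ABR with time run to the ET/EOS visit may be added as a sensitivity analysis. It should not be the main rule, because it leaves about half of the excess when treatment stops at 50 exposure days of any kind.

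The cost is a short text change in two places and the matching programming. The downside is that a few treated bleeds after the last regular dose leave the ABR. Dosing, visits and data collection do not change.

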### 5.3.3. Treatment Regimen Changes

In the following sections, new treatment regimen refers to the regimen to which the patient has changed, and the previous treatment regimen refers to the regimen immediately before the new treatment regimen. The start date and time of the new treatment regimen and the end date and time of the previous treatment regimen are defined in the following scenarios:

- From an episodic regimen to a prophylactic regimen: The prophylactic regimen starts at the date and time of the first prophylactic dose in the prophylactic regimen. The episodic regimen ends 1 minute before that. If the time of the first prophylactic dose in the prophylactic regimen is not available, the prophylactic regimen will start at 00:01 on the day of the first prophylactic dose in the prophylactic regimen, and the episodic regimen will end at 23:59 on the day prior to that.
- From a prophylactic regimen to an episodic regimen: The prophylactic regimen ends at the date and time of the last prophylactic dose in the prophylactic regimen. The episodic regimen starts 1 minute after that. If the time of the last prophylactic dose in the prophylactic regimen is not available, the prophylactic regimen will end at 23:59 on the day of the last prophylactic dose in the prophylactic regimen, and the episodic regimen will start at 00:01 on the next day.
- From an episodic regimen to an ITI regimen: The ITI regimen starts at the date and time of the first ITI dose in the ITI regimen. The episodic regimen ends 1 minute before that. If the time of the first ITI dose in the ITI regimen is not available, the ITI regimen will start at 00:01 on the day of the first ITI dose in the ITI regimen, and the episodic regimen will end at 23:59 on the day prior to that.
- From a prophylactic regimen to an ITI regimen: If there is no prophylactic dose on the day of the treatment regimen change recorded in the eCRF, the ITI regimen starts at

	Statistical Analysis Plan	Final v1.0
---	----------------------------------	-------------------

00:01 on the day of treatment regimen change, and the prophylactic regimen ends at 23:59 on the day prior to the day of treatment regimen change. If there is a prophylactic dose on the day of treatment regimen change, the ITI regimen starts 1 minute after that prophylactic dose, and the prophylactic regimen ends on the date and time of that prophylactic dose.

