5.3. Rationale for Dose and Schedule Selection

Results of the Phase 1/2a study (Study SYN-FIXFc-07-001) evaluating the safety and PK of a single dose of rFIXFc suggested that rFIXFc is well tolerated when given as a single dose at doses ranging from 1 to 100 IU/kg. In the completed Phase 3 study (Study 998HB102), multiple doses between 20 and 100 IU/kg were generally well tolerated, with an AE profile generally consistent with that expected in patients with hemophilia B. No dose-limiting toxicity (DLT) has been identified to date in humans receiving a dose of rFIXFc up to 100 IU/kg.

The recommended starting prophylactic dose of rFIXFc in this study, approximately 50 IU/kg weekly, is based on the data from the Phase 1/2a and Phase 3 studies (including pediatric PK data from subjects <12 years of age) and knowledge of increased clearance of factor concentrates in children (Table 1). This dose is predicted to maintain trough levels >1% in 99% of pediatric subjects. Adjustments to the dose and interval of rFIXFc can be made in this study based on available PK data, subsequent FIX activity levels, level of physical activity, and bleeding pattern, in accordance with local standards of care for a prophylactic regimen.

The dose for treatment of bleeding episodes will target peak plasma FIX activity of approximately 30% to 100%, in accordance with local standards (see guidance provided in Appendix A), and taking into account lower rFIXFc recoveries observed in young children (Table 1). Subjects developing positive low titer inhibitors may continue on study at the same or higher dose per injection of rFIXFc at the discretion of the Investigator (see Section 10.2.6.2).

If a subject requires surgery while participating in this study, the subject may be treated with the dose and regimen of rFIXFc deemed appropriate for the type of surgery. All major surgeries will be reported as serious adverse events (SAEs).

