#### 5.1.1. Data Presentation

In general, presentations of background/demography and safety data will include an overall/total column and those for efficacy and health outcome data will not. Any exceptions to this are specified in the relevant section.

There is only 1 treatment arm in the study. However, unless otherwise stated, all analyses and background/demography tables will be presented for the following treatment groups, as defined in Section 3.1.2:

- Patients who were ever on an episodic regimen
- Patients who were ever on a prophylactic regimen
- Patients who were ever on an ITI regimen

For longitudinal data, the safety or efficacy periods included for these groups is the time spent on that regimen within that period. These periods are defined in Section 5.3 and 5.4.

Selected tables will also be presented by patients’ inhibitor development status, if there are at least 5 patients in the positive inhibitor subgroup (defined as in Section 5.2.4).

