### 5.3.1. Start Date and Time of the First Treatment Regimen

The start date and time of the first treatment regimen is defined as either:

- The date and time of the first rFIXFc dose for patients beginning on a prophylactic treatment regimen, as per the treatment assignment eCRF data.
- The date and time 120 hours after the date and time of the baseline PK dose for patients beginning on an episodic treatment regimen, as per the treatment assignment eCRF data.

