#### **5.4.2.2. Adjustments Due to Large Injection Intervals**

For analysis purposes, the efficacy period will also be adjusted to account for large intervals between injections resulting from missing data. A large interval is defined as >28 days between any 2 adjacent rFIXFc injections within a prophylactic treatment regimen and any such intervals will be removed from the efficacy period. The efficacy period prior to each such interval will end at the time of the first injection of this interval and restart (or start if it is the first interval of a treatment regimen) at the time of the second injection of this interval. The efficacy period will be adjusted for each identified interval that is not within a surgical/rehabilitation period. This algorithm applies only to prophylactic regimens and no adjustment for large injection intervals will be made for episodic treatment regimens.

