#### **5.4.5. Safety Period**

The overall safety period is defined as beginning at the first dose of study medication rFIXFc. For patients who are subsequently enrolled, the safety period ends on the date of the Final Safety Follow-up Visit (by telephone or in person), 14 (+7) days after the last dose of rFIXFc. For patients who fail screening, this period ends on the date that this is confirmed.

The safety period on a specific treatment regimen is as described in Section 5.3 except that the end of the patient's last treatment regimen is the end of their safety period.

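### SAP 5.3.3 counts a child who returns from prophylaxis to episodic treatment as episodic from 1 minute after the last prophylactic dose, while SAP 5.3.1 waits 120 hours after the baseline dose

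*SAP*

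**What the plan says.** **The switch rule.** SAP 5.3.3 ends prophylaxis, on a move to episodic treatment, at the time of the "last prophylactic dose in the prophylactic regimen. The episodic regimen starts 1 minute after that". If the clock time of that dose is missing, "the prophylactic regimen will end at 23:59 on the day of the last prophylactic dose in the prophylactic regimen" and episodic time opens at 00:01 the next day.

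**The start rule.** For a child whose first regimen is episodic, SAP 5.3.1 sets a different start: "The date and time 120 hours after the date and time of the baseline PK dose for patients beginning on an episodic treatment regimen".

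**Where these dates go.**
- SAP 5.4.2 takes each regimen's efficacy period from the regimen dates. Its only exceptions are for surgery and for gaps of more than 28 days within prophylaxis; on the latter, SAP 5.4.2.2 adds that "no adjustment for large injection intervals will be made for episodic treatment regimens".
- SAP 5.4.5 does the same for safety: "The safety period on a specific treatment regimen is as described in Section 5.3", except that a patient's last regimen is extended to the end of follow-up.
- SAP 5.1.1 then builds the by-regimen tables, in which "the safety or efficacy periods included for these groups is the time spent on that regimen within that period".

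**Cover from a prophylactic dose.** The recommended starting regimen is 50 IU/kg weekly (Protocol 7.3.2). Protocol 5.3 says of it: "This dose is predicted to maintain trough levels >1% in 99% of pediatric subjects".

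**ITI.** When prophylaxis gives way to ITI, SAP 5.3.3 starts ITI 1 minute after a prophylactic dose given on the change day, or at 00:01 on that day if there was none. SAP 5.4.4 starts the ITI period at the first ITI dose.

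**The concern.** The week after a prophylactic dose is, on the protocol's own account, a week with factor IX above the target trough. At this one switch the SAP credits that week to the regimen that did not supply the dose. Three things follow for the child concerned:

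- Covered days, in which few bleeds are expected, lengthen the episodic denominator and pull the episodic ABR down.
- A breakthrough bleed in those days is charged to episodic treatment.
- An adverse event starting on a later day of that interval appears in the episodic column.

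ABR is a secondary endpoint computed per patient in a study of about 30. SAP 5.1.1 says efficacy presentations will generally have no overall column, so the regimen columns are the main ABR display. SAP 5.4.2 makes an episodic period evaluable after a single day, so a short episodic spell could consist entirely of covered time.

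**Working it through.** The documents state no figure that depends on this rule, so there is nothing to reproduce. The check traces the rule, asks whether the reassigned time is covered, and then sizes the effect.

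**1. The two lags.** SAP 5.3.1: 120 h × 60 = 7,200 minutes. SAP 5.3.3: 1 minute. No rule in SAP 5.3 or 5.4 corrects the second.

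**2. Is the time covered?** Inputs are from Protocol Table 1, under 6 years, geometric means: incremental recovery 0.590 IU/dL per IU/kg, half-life 66.49 h, dose-normalized AUC 22.71. With single-exponential decay and no endogenous activity,

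activity(t) = 50 × 0.590 × 0.5^(t/66.49)

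| Hours after dose | 0 | 24 | 72 | 120 | 168 |
|---|---|---|---|---|---|
| IU/dL | 29.5 | 23.0 | 13.9 | 8.4 | 5.1 |

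With the lower confidence limits of both parameters (0.515 and 55.86 h), the values are 5.8 at 120 h and 3.2 at 168 h.

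This curve is generous. It implies an AUC of 29.5 × 66.49 / ln 2 ≈ 2,830, whereas Table 1 gives 50 × 22.71 ≈ 1,136. Scaling the curve to the Table 1 AUC gives a starting value of 1,136 × ln 2 / 66.49 ≈ 11.8 IU/dL, hence 3.4 at 120 h and 2.1 at 168 h. On either version the weekly interval stays above 1 IU/dL, in line with the protocol's prediction. "Covered" here means above that 1% level, not constant activity.

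**3. Effect on a switcher's episodic ABR.** Let D be episodic days, c the covered days within them, and assume covered time carries 20% of the off-cover bleed rate. The 20% comes from the more than 80% ABR reduction in Study 998HB102 (Protocol 5.1.4). Then

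expected ABR / off-cover ABR = [0.2c + (D − c)] / D = 1 − 0.8 c/D

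D is an assumption, since the documents give no length for such spells. c is 5 days (the SAP's own 120 h) or 7 days (the recommended interval).

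| Understatement | D = 28 | D = 56 | D = 84 |
|---|---|---|---|
| c = 5 | 14.3% | 7.1% | 4.8% |
| c = 7 | 20.0% | 10.0% | 6.7% |

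A cross-check uses the illustrative rates in Protocol 5.1.1: about 20 bleeds a year on episodic treatment and 3 to 4 (spontaneous only) on prophylaxis. For c = 7 and D = 28, (7 × 3 + 21 × 20)/28 = 15.75 and (7 × 4 + 21 × 20)/28 = 16.0, against 20 off cover. For c = 5 and D = 84 the same formula gives 19.0 to 19.1. The range agrees.

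**4. With pooling.** SAP 5.3.4 adds together all time on the same regimen. Suppose the child had 26 earlier episodic weeks (an assumption) and then a 4-week return, so D = 182 + 28 = 210. The understatement is 0.8 × 5/210 = 1.9% to 0.8 × 7/210 = 2.7%.

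**5. Extreme case.** A child who began on prophylaxis and then had only 5 episodic days would have an episodic ABR made up wholly of covered time: 0 with no bleed, or 365.25/5 ≈ 73 with one.

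**The case against.** The strongest objection is reach. Episodic treatment is offered before prophylaxis (Protocol 7.1 and 7.3.2), and SAP 3.1.2 calls prophylaxis required for all patients. SAP 3.1.2.2 has it continue until 50 exposure days, discontinuation, ITI or the end of study, and a return to episodic treatment is not on that list. If nobody returns, the rule does nothing. This stands and limits the importance of the point. Still, the SAP writes a rule for the switch, and the rule misallocates time whenever it is used.

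Several stronger readings are tempting and are not supported:

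- *Reactions that end prophylaxis move to the episodic column.* A Grade 2 or greater allergic reaction requires withdrawal (Protocol 11), not a switch. Prophylaxis then remains the last regimen, and SAP 5.4.5 extends it through follow-up. SAP 9.3.1 also leaves open whether adverse-event onset time is collected, so minute-level misplacement of same-day events is not established. If the dose time is missing, same-day events stay with prophylaxis. Events on later days of the window are still booked as episodic.
- *The study's main safety results are affected.* The primary inhibitor analysis counts patients (SAP 9.4.3.2), and safety tables generally carry an overall column (SAP 5.1.1). Neither changes.
- *The 120 hours is a stated washout for carry-over.* SAP 5.3.1 gives no reason for it, and SAP 6.6 says PK doses are not used to prevent or treat bleeding. Only the inconsistency can be asserted.
- *The 120 hours should become prophylactic efficacy time.* That would break the SAP's own convention. Prophylactic efficacy time ends at the last dose at study end (SAP 5.3.2), before surgery (5.4.2.1) and before long gaps (5.4.2.2). For episodic starters under 5.3.1, those hours precede any regimen.

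It is also fair that the 80% reduction comes from previously treated patients aged 12 or older and that all summaries are descriptive. The cover calculation does not carry over to children with inhibitors, so the ITI point rests only on the conflict between SAP 5.3.3 and 5.4.4.

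**Conclusion.** The inconsistency is real but narrow. For a child who goes from prophylaxis to episodic treatment, SAP 5.3.3 puts covered time, and the bleeds and later-day adverse events within it, under the episodic regimen, and no other rule removes them.

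The expected understatement of that child's episodic ABR is about 5% to 20% for a spell of 4 to 12 weeks with no earlier episodic time, and about 2% to 3% when a long earlier spell is pooled. These figures rest on 5 to 7 covered days, a 20% residual bleed rate and assumed spell lengths. An individual ABR may move either way if a breakthrough bleed falls in the window. The effect on the summary tables cannot be sized because the number of switchers is not given; it is nil if there are none. Only the by-regimen summaries are exposed.

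The ITI start is a separate conflict between two SAP sections.

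**What to change.** In SAP 5.3.3, prophylaxis to episodic:

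- Start episodic efficacy time 120 hours after the last prophylactic dose, matching 5.3.1.
- Leave those 120 hours, and any bleeds in them, out of both regimens' efficacy periods, and list such bleeds.
- In by-regimen safety tables, keep adverse events with onset in that window under prophylaxis.

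Separately, reconcile the prophylaxis-to-ITI bullet with SAP 5.4.4, so that the ITI analysis period starts at the first ITI dose. It should not start 1 minute after a same-day prophylactic dose or at 00:01 on the change day.

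The cost is a sentence or two and a small programming change. Switchers lose up to 5 days of episodic time, and a very short spell may cease to be evaluable. Some cover remains after 120 hours (step 2 above), so the change makes the SAP consistent and removes most of the dilution, not all of it. It concerns analysis windows only and leaves treatment unchanged.
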